#### Physician’s global assessment of fingernail disease severity (VAS)

The physician’s assessment of nail disease activity will be performed using 100 mm VAS ranging from no disease activity to maximal disease activity, after the question *“After you have*

*viewed all the fingernails of a subject, consider all aspects of the subject's fingernails and place a vertical line on the scale giving a global assessment of their fingernails".*

## 2.5.2 Description of Health-related Quality of Life Endpoints

### SF-36

The Short Form Health Survey (SF-36) is a widely used and extensively studied instrument to measure health-related quality of life among healthy subjects and patients with acute and chronic conditions. It consists of eight subscales that can be scored individually: Physical Functioning, Role-Physical, Bodily Pain, General Health, Vitality, Social Functioning, Role-Emotional, and Mental Health. Two overall summary scores, the Physical Component Summary (PCS) and the Mental Component Summary (MCS) also can be computed. The SF-36 has proven useful in monitoring general and specific populations, comparing the relative burden of different disease, differentiating the health benefits produced by different treatments, and in screening individual patients. The eight domains are based on a scale from 0-100 while PCS and MCS are norm-based scores with a mean of 50 and a standard deviation of 10.

[figure not shown]
### FACIT - Fatigue

[figure not shown]
The Functional Assessment of Chronic Illness Therapy – Fatigue (FACIT-Fatigue©) is a 13-item questionnaire that assesses self-reported fatigue and its impact upon daily activities and function.

Subjects respond to each item on a 5-point Likert-type scale (0 = not at all; 1 = a little bit; 2 = somewhat; 3 = quite a bit; 4 = very much) based on their experience of fatigue during the past 2 weeks. The scale score is computed by summing the item scores, after reversing those items that are worded in the negative direction. Numbering the questions from 1 to 13, it is evident that questions 7 and 8 are worded in the positive direction (4 indicates a desirable response) and all other questions are worded in the negative directions (4 indicates an undesirable response). Thus, it is necessary to reverse the responses for all but questions 7 and 8 (i.e. original response of 0 gets mapped to 4, 1=3, 2=2, 3=1, and 4=0) for scoring purposes.

When there are missing item scores, the subscale score was computed by summing the non-missing item scores, multiplying by 13 (the total number of items in the scale) and dividing by the number of non-missing items (i.e. normalizing the results). The latter rule applied only when at least half of the items (seven or more) are non-missing.

FACIT Fatigue subscale scores range from 0 to 52, where higher scores represent less fatigue ([Cella D et al., 2004](#)).

[figure not shown]

### 2.5.3 Handling of missing data

[figure not shown]
#### Missing data

Missing data for primary and key secondary binary efficacy variables for data up to Week 52 will be handled as follows:

- Subjects who drop out of the trial for any reason will be considered non-responders from the time they drop out through Week 52 for active groups or through Week 16 for placebo group.
- Subjects who do not have the required data at baseline and at the specific time point to compute response will be classified as non-responders.

Data collected after Week 16 will generally be presented as 'observed case'; i.e. all available data for each time point will be included in the analyses. In addition, multiple imputation will be used for ACR50. These will be presented for AIN457 6mg/kg - 3mg/kg treatment group only. Observed data summary will be presented by treatment sequence ([Section 2.2.2](#)).

## **2.7 Safety analyses**

Summaries will be performed for the entire treatment period. Safety analyses will be performed on treatment received or actual treatment as described below:

The actual treatment or treatment received for summaries of safety data will differ to the treatment assigned at randomization only if a subject received the wrong treatment during the entire study.

Subjects who switch treatment during the study (e.g. from placebo to active treatment) will be counted to both groups using the appropriate start and stop exposure date.

### **2.7.1 Adverse events (AEs)**

Treatment emergent AEs (events that started after the first dose of study treatment or events present prior to the first dose of study treatment but increased in severity based on preferred term) will be summarized up to 12 weeks (84 days) after the last dose.

AEs will be summarized by presenting, for each treatment group, the number and percentage of subjects having any AE, having an AE in each primary system organ class and having each individual AE (preferred term). Summaries will also be presented for AEs by severity and for study treatment related AEs. If a subject reported more than one AE with the same preferred term, the AE with the greatest severity will be presented. If a subject reported more than one AE within the same primary system organ class, the subject will be counted only once with the

greatest severity at the system organ class level, where applicable. SAEs will also be summarized.

As appropriate, the incidence of AEs will be presented per 100 subject years of exposure.

Separate summaries will be provided for death, SAE, other significant AEs leading to discontinuation and AEs leading to dose adjustment (including study treatment discontinuation).

Adverse events reported will be presented in descending frequency according to its incidence in i.v. secukinumab group starting from the most common event. Summaries (crude incidences only) will also be presented for AEs by severity and for study treatment related AEs. If a particular AE 'severity' is missing, this variable will be listed as missing and treated as missing in summaries. If a subject reported more than one adverse event with the same preferred term, the adverse event with the greatest severity will be presented. If a subject reported more than one adverse event within the same primary system organ class, the subject will be counted only once with the greatest severity at the system organ class level, where applicable.

Separate summaries will be provided for adverse events suspected to be related to study drug, deaths, serious adverse events, and adverse events leading to discontinuation and adverse events leading to temporary dose interruption.

Adverse events will also be reported separately by SMQ according to MedDRA. The MedDRA version used for reporting the study will be described in a footnote.

Non-treatment emergent adverse events will be listed.

Algorithms for date imputations will be provided in Programming Datasets Specifications.

For serious adverse events (SAEs) occurred during screening a listing will be prepared for all subjects screened including screening failures.

The safety analyses that will be performed for treatment emergent AEs and on treatment labs and vital signs for each analysis period is described in [Table 2-4](#).

**Table 2-4      Overview of analyses on some safety endpoints**

Analysis period	AEs & SAEs	AEs by severity	Study drug related AEs	AEs-SMQ	Risk
Day 1 – Week 16	crude incidence	crude incidence	crude incidence	crude incidence	crude incidence
Entire Treatment	crude incidence exposure time adjusted incidence*	crude incidence	crude incidence	exposure time adjusted incidence	crude incidence exposure time adjusted incidence

Analysis period	AEs & SAEs	AEs by severity	Study drug related AEs	AEs-SMQ	Risk
-----------------	------------	-----------------	------------------------	---------	------

\*Exposure-adjusted incidence rates will be done for the following :  
at the PSOC for AE and SAE and Level 1 for Risks and SMQ analyses  
at the PT level for common AEs, which is defined as at least 2% of the patients in the i.v. secukinumab during the initial treatment period or events that had an incidence rate of at least 5.0 cases per 100 subject-years in the combined i.v. secukinumab groups during the entire treatment period

## 2.7.2 Laboratory data

The summary of lab data will only include on treatment data, which are defined as those lab assessments after the first dose of study treatment and on or before last dose + 84 days.

The summary of laboratory evaluations will be presented for three groups of laboratory tests (hematology, chemistry and urinalysis). In addition to the individual laboratory parameters the ratios “total cholesterol / HDL” and “apolipoprotein B / apolipoprotein A1” will be derived and summarized.

For urinalysis, frequency tables will be presented.

Descriptive summary statistics for the change from baseline to each study visit will be presented. These descriptive summaries will be presented by laboratory test and treatment group. Change from baseline will only be summarized for subjects with both baseline and post baseline values and will be calculated as:

change from baseline = post baseline value – baseline value

For each parameter, the maximum change (maximum decrease and maximum increase) from baseline, will be analyzed analogously.

In addition, shift tables may be provided for parameters to compare a subject's baseline laboratory evaluation relative to the visit's observed value. For the shift tables, the normal laboratory ranges will be used to evaluate whether a particular laboratory test value was normal, low, or high for each visit value relative to whether or not the baseline value was normal, low, or high. If appropriate, the shifts to the most extreme laboratory test value within a treatment phase will be presented as well (including category “high and low”). These summaries will be presented by laboratory test and treatment group.

The following laboratory parameters will be analyzed with respect to numerical Common Terminology Criteria for Adverse Events (CTCAE) grades, given in [Table 2-5](#): hemoglobin, platelets, white blood cell count, neutrophils, lymphocytes, creatinine, total bilirubin (TBL), gamma-glutamyl transferase (GGT), alanine aminotransferase (ALT), aspartate aminotransferase (AST), alkaline phosphatase (ALP), glucose, cholesterol, triglycerides (TG).

These summaries will be split into hematology and chemistry.

**Table 2-6 Liver-related events**

Parameter	Criterion
ALT	>3xULN; >5xULN; >8xULN; >10xULN, >20xULN
AST	>3xULN; >5xULN; >8xULN >10xULN; >20xULN
ALT or AST	>3xULN; >5xULN; >8xULN >10xULN; >20xULN
TBL	>1.5xULN, >2xULN, >3xULN,
ALP	>2xULN, >3xULN. >5xULN
ALT or AST & TBL	ALT or AST >3xULN & TBL >2xULN; ALT or AST >5xULN & TBL >2xULN; ALT or AST >8xULN & TBL >2xULN; ALT or AST >10xULN & TBL >2xULN
ALP & TBL	ALP >3xULN & TBL >2xULN ALP >5xULN & TBL >2xULN
ALT or AST & TBL & ALP	ALT or AST >3xULN & TBL >2xULN & ALP <2xULN ( Hy's Law ) Note: elevated ALP may suggest obstruction as a consequence of gall bladder or bile duct disease; ALP may also be increased in malignancy. FDA therefore terms Hy's Law cases as indicators of pure hepatocellular injury . This does not mean that cases of ALT or AST >3xULN & TBL >2xULN & ALP $\geq$ 2xULN may not result in severe DILI.

Notes:

- 1) In studies which enroll subjects with pre-existing liver disease, baseline LFT may be increased above ULN; in such a case it is meaningful to add the condition "and worse than baseline" to the abnormality criteria

For a combined criterion to be fulfilled, all conditions have to be fulfilled on the same visit. The criteria are not mutually exclusive, e.g. a subject with ALT = 6.42xULN is counted for ALT >3xULN and ALT >5x ULN.

Individual subject data listings may be provided for subjects with abnormal laboratory data. Data of subjects with newly occurring or worsening liver enzyme abnormalities may be listed in an additional listing.

The laboratory values below Lower Level of Quantification (LLQ) or above Upper Level of Quantification (ULQ) will be imputed as LLQ or ULQ, respectively. The numerical part of the reported result will be treated as the actual LLQ or ULQ.

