16.11 Appendix 11: Liver event and laboratory trigger definitions and follow-up requirements

Table 16-4 Liver Event and Laboratory Trigger Definitions

	Definition/ threshold
LIVER LABORATORY TRIGGERS	$3 \times \text{ULN} < \text{ALT} / \text{AST} \leq 5 \times \text{ULN}$ $1.5 \times \text{ULN} < \text{TBL} \leq 2 \times \text{ULN}$
LIVER EVENTS	$\text{ALT or AST} > 5 \times \text{ULN}$ $\text{ALP} > 2 \times \text{ULN}$ (in the absence of known bone pathology) $\text{TBL} > 2 \times \text{ULN}$ (in the absence of known Gilbert syndrome)

ALT or AST > 3 × ULN and INR > 1.5
Potential Hy's Law cases (defined as ALT or AST > 3 × ULN and TBL > 2 × ULN [mainly conjugated fraction] without notable increase in ALP to > 2 × ULN)
Any clinical event of jaundice (or equivalent term)
ALT or AST > 3 × ULN accompanied by (general) malaise, fatigue, abdominal pain, nausea, or vomiting, or rash with eosinophilia
Any adverse event potentially indicative of a liver toxicity *

* These events cover the following: hepatic failure, fibrosis and cirrhosis, and other liver damage-related conditions; non-infectious hepatitis; benign, malignant and unspecified liver neoplasms

TBL: total bilirubin; ULN: upper limit of normal

Table 16-5 Follow up Requirements for Liver Events and Laboratory Triggers

Criteria	Actions required	Follow-up monitoring
Potential Hy's Law case ^a	Discontinue the study drug immediately Hospitalize, if clinically appropriate Establish causality Complete liver eCRF	ALT, AST, TBL, Alb, PT/INR, ALP and γGT until resolution ^c (frequency at investigator discretion)
ALT or AST		
> 8 × ULN	Discontinue the study drug immediately Hospitalize if clinically appropriate Establish causality Complete liver eCRF	ALT, AST, TBL, Alb, PT/INR, ALP and γGT until resolution ^c (frequency at investigator discretion)
> 3 × ULN and INR > 1.5	Discontinue the study drug immediately Hospitalize, if clinically appropriate Establish causality Complete liver eCRF	ALT, AST, TBL, Alb, PT/INR, ALP and γGT until resolution ^c (frequency at investigator discretion)
> 5 to ≤ 8 × ULN	Repeat LFT within 48 hours If elevation persists, continue follow-up monitoring If elevation persists for more than 2 weeks , discontinue the study drug Establish causality Complete liver eCRF	ALT, AST, TBL, Alb, PT/INR, ALP and γGT until resolution ^c (frequency at investigator discretion)

Criteria	Actions required	Follow-up monitoring

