> 3 × ULN accompanied by symptoms ^b	Discontinue the study drug immediately Hospitalize if clinically appropriate Establish causality Complete liver eCRF	ALT, AST, TBL, Alb, PT/INR, ALP and γGT until resolution ^c (frequency at investigator discretion)
> 3 to ≤ 5 × ULN (patient is asymptomatic)	Repeat LFT within the next week If elevation is confirmed, initiate close observation of the patient	Investigator discretion Monitor LFT within 1 to 4 weeks
ALP (isolated)		
> 2 × ULN (in the absence of known bone pathology)	Repeat LFT within 48 hours If elevation persists, establish causality Complete liver eCRF	Investigator discretion Monitor LFT within 1 to 4 weeks or at next visit
TBL (isolated)		
> 2 × ULN (in the absence of known Gilbert syndrome)	Repeat LFT within 48 hours If elevation persists, discontinue the study drug immediately Hospitalize if clinically appropriate Establish causality Complete liver eCRF	ALT, AST, TBL, Alb, PT/INR, ALP and γGT until resolution ^c (frequency at investigator discretion) Test for hemolysis (e.g., reticulocytes, haptoglobin, unconjugated [indirect] bilirubin)
> 1.5 to ≤ 2 × ULN (patient is asymptomatic)	Repeat LFT within the next week If elevation is confirmed, initiate close observation of the patient	Investigator discretion Monitor LFT within 1 to 4 weeks or at next visit
Jaundice	Discontinue the study drug immediately Hospitalize the patient Establish causality Complete liver eCRF	ALT, AST, TBL, Alb, PT/INR, ALP and γGT until resolution ^c (frequency at investigator discretion)
Any AE potentially indicative of a liver toxicity*	Consider study drug interruption or discontinuation Hospitalization if clinically appropriate Establish causality Complete liver eCRF	Investigator discretion

* These events cover the following: hepatic failure, fibrosis and cirrhosis, and other liver damage-related conditions; non-infectious hepatitis; benign, malignant and unspecified liver neoplasms

TBL: total bilirubin; ULN: upper limit of normal

^a Elevated ALT/AST > 3 × ULN and TBL > 2 × ULN but without notable increase in ALP to > 2 × ULN

^b (General) malaise, fatigue, abdominal pain, nausea, or vomiting, or rash with eosinophilia

Criteria	Actions required	Follow-up monitoring

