Post-baseline safety	Notable abnormalities (e.g. lab)	The most extreme measurement in the window will be used. Note this means a patient can have a notably high and notably low measurement within a window.

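### The SAP counts Hy's Law and other combined liver criteria only within one undefined visit, a condition absent from the protocol, so non-concurrent cases can drop out of the summary rows

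*SAP*

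**What the plan says.** **SAP.** Table 2-6 in section 2.7.2 lists single-parameter rows (ALT, AST, TBL, ALP) and combined rows. The Hy's Law row reads "ALT or AST >3xULN & TBL >2xULN & ALP <2xULN". The text below the table adds: "For a combined criterion to be fulfilled, all conditions have to be fulfilled on the same visit". Visit is not defined there.

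The SAP appendix has two rules that might bear on it. Section 4.1.1 maps repeat and unscheduled assessments to analysis windows in the same way as scheduled ones. For notable abnormalities, Table 4-2 says: "The most extreme measurement in the window will be used". Neither rule is stated to govern the combined rows of Table 2-6.

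**Protocol.** Appendix 11 defines a potential Hy's Law case in Table 16-4 and again in the footnote to Table 16-5: "Elevated ALT/AST > 3 × ULN and TBL > 2 × ULN but without notable increase in ALP to > 2 × ULN". Neither text has a same-visit or same-date condition. Table 16-5 also calls for repeat liver tests, some under "Repeat LFT within 48 hours" and some under "Repeat LFT within the next week", which will often fall on unscheduled dates.

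**The concern.** The SAP adds a concurrency condition that the protocol definition lacks. SAP section 1 says that deviations from the protocol are documented, but this addition is not flagged. If bilirubin rises after the transaminases have already come down, no single visit meets every condition, and the subject is not counted in the ALT/AST-with-TBL row or the Hy's Law row.

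The single-parameter rows do not repair this. They count ALT and TBL separately and do not show that both elevations occurred in one subject. These rows are the main summary of possible hepatotoxicity in a study meant to support registration (protocol section 1.2). Such events are few, so one subject more or less changes what is reported.

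**Working it through.** The plan states no figure to reproduce. The check is what the rule does under each meaning of visit.

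**Inputs.** Blood chemistry is Group 3 in SAP Table 4-1; its target days and limits are below. On-treatment laboratory data end at last dose + 84 days (SAP 2.7.2). The last planned dose is at Week 48 (protocol 6.1.3), target Day 337. A repeat liver test is a full panel of ALT, AST, TBL, PT/INR, ALP and GGT (protocol 10.2.1).

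**Reading 1: nominal visit or sample date.** Suppose ALT is above 3xULN at one draw, and TBL first exceeds 2xULN at a later draw when ALT and AST are at 3xULN or below. No single visit meets both conditions, so the subject is not counted. If ALT or AST is still above 3xULN at the later draw, that draw qualifies alone, subject to the ALP limit in the Hy's Law row.

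**Reading 2: analysis window, most extreme value used.** Width = upper − lower + 1. Room = upper − target. Gap = next target − target.

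| Visit | Target | Window | Width | Room after target | Gap to next chemistry draw |
|---|---|---|---|---|---|
| Week 4 | 29 | 2–43 | 42 | 14 | 28 |
| Week 8 | 57 | 44–71 | 28 | 14 | 28 |
| Week 12 | 85 | 72–99 | 28 | 14 | 28 |
| Week 16 | 113 | 100–141 | 42 | 28 | 56 |
| Week 24 | 169 | 142–183 | 42 | 14 | 28 |
| Week 28 | 197 | 184–239 | 56 | 42 | 84 |
| Week 40 | 281 | 240–323 | 84 | 42 | 84 |
| Week 52 | 365 | 324–439 | 116 | 74 | – |

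- *Repeats.* The smallest room is 14 days. A repeat 2 or 7 days after an on-target draw stays in the same window at all eight visits and can complete the criterion.
- *Later rise.* A rise first seen 15 days after an on-target draw at Week 4, 8, 12 or 24 is in the next window. The gap exceeds the room at every visit that has a successor, so a rise first seen at the next on-target draw is never in the same window.
- *Edges.* Days 239 and 240 are one day apart but fall in different windows.
- *Longest lag, on-schedule subject.* On-treatment data end at Day 337 + 84 = 421. Within the Week 52 window the largest lag is 421 − 324 = 97 days. It needs off-schedule samples at both ends, since Day 324 is no chemistry target day and SAP 4.1.1 keeps the follow-up visit out of the window mapping.
- *ALP.* Taking the most extreme ALP in the window could also remove a Hy's Law case, if ALP reached 2xULN on a different date.

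**Comparison.** Reading 1 excludes every non-concurrent case. Reading 2 includes or excludes it according to where a window edge falls.

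**The case against.** The strongest reply is that little is lost, and it has four parts.

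1. *Repeats are full panels.* A reader might infer that every case with a repeat on another date is missed. The documents do not support that. The repeat measures ALT, AST, TBL and ALP together and can meet the criterion alone, and under window mapping the 48-hour and one-week repeats normally share the window. The gap is confined to bilirubin rising after ALT and AST have fallen to 3xULN or below, or to ALP differing between dates. This part stands.

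2. *The window width overstates the lag.* A reader might take the full span, 439 − 324 = 115 days. That assumes the most-extreme rule governs Table 2-6, which the SAP does not say. It also needs a last dose on or after Day 439 − 84 = 355, which is 18 days past the Week 48 target. For an on-schedule subject the ceiling is about 97 days. This part stands.

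3. *The protocol is silent, not contrary.* It does not say that non-concurrent values count, so a flat contradiction cannot be claimed. This stands, but an added and undefined restriction still needs to be explained.

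4. *Cases are captured elsewhere.* Table 16-5 requires a liver eCRF for potential Hy's Law cases, liver events are recorded as AEs (protocol 10.2.1), worst-grade CTCAE shifts are planned, and SAP 4.1.1 says all collected data will be listed. So a reader should not infer that cases vanish from the safety database. This stands. However, the specific listing of subjects with liver enzyme abnormalities in SAP 2.7.2 is optional, and no planned summary row shows both elevations in one subject at different visits.

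**Conclusion.** The point holds in a limited form. The same-visit condition has no counterpart in the protocol definition, and visit is undefined. A subject whose TBL first exceeds 2xULN after ALT and AST have fallen to 3xULN or below can be left out of the combined and Hy's Law rows. Under a nominal-visit or sample-date reading this always happens; under the window reading it happens when the two values straddle a window edge.

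The effect is on a descriptive summary table, not on case capture. The documents give no event rates and no distribution of the lag between ALT and TBL, so the number of subjects affected cannot be computed. The 97-day figure assumes the window reading, the most-extreme rule and dosing on schedule. This is a worthwhile, inexpensive improvement to the reported hepatotoxicity counts, not a flaw that undermines the safety analysis.

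**What to change.** In SAP 2.7.2:

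- Define visit for the combined rows of Table 2-6 as the sample date, and keep the same-visit count on that basis.
- Alongside it, add a prespecified count or table of subjects with peak ALT or AST >3xULN and peak TBL >2xULN at any time on treatment (up to last dose + 84 days), including unscheduled samples. The documents give no basis for a fixed number of days between the two peaks, so none is proposed.
- Make the listing of these subjects mandatory, with sample dates and ALP, so that timing and cholestasis can be judged case by case.
- In the same edit, align the ALP limit. At exactly 2xULN a subject fails the SAP row (ALP below 2xULN) but meets the protocol wording (no increase above 2xULN).

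The cost is one derivation, one table and one listing. The downside is a few more candidate cases to review, some with elevations far apart in time, which the listed dates will show.
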